3.4.1 Definition of endpoint(s)

For PASI and sPGA related endpoints, please refer to [Section 3.2](#) and [Section 3.3](#) for the definition of scores.

➤ **Changes in affected BSA (%) from baseline to Week 4, 8 and 12.**

This is a continuous endpoint based on BSA defined as below.

Body Surface Area (BSA)

BSA will be calculated from the integrated BSA within the PASI assessment.

Percent BSA will be evaluated as the percent involvement of psoriasis on each patient's BSA on a continuous scale from 0% (no involvement) to 100% (full involvement), where 1% corresponds to the size of the patient's hand (including the palm, fingers, and thumb).

➤ **Change in Dermatology Life Quality Index (DLQI) from baseline to Week 12.**

This is a continuous endpoint based on DLQI defined as below.

[figure not shown]
Dermatology Life Quality Index (DLQI)

[figure not shown]
The DLQI is one of the most widely used measures in dermatology populations to evaluate participants' Health-Related Quality of Life. It is a patient-reported outcome instrument consisting of 10 items exploring six dimensions: 'Symptoms and feelings' (2 items), 'Daily activities' (2 items), 'Leisure' (2 items), 'Work and school' (1 item), 'Personal relationships' (2 items), 'Treatment' (1 item). Each item is rated on a dichotomous: Yes/No and 3- and 4-point Likert/Likert-type scale for capturing skin symptom-related experiences over the previous weeks.

[figure not shown]
Scores are computed overall and for the six domains. The total DLQI score ranges from 0 to 30, the higher the score, the greater the impairment of quality of life.

[figure not shown]
If one of the 10 items are left unanswered, it is scored 0 and the scores are summed and expressed as usual out of a maximum of 30. If two or more of the ten items are left unanswered, DLQI total score will be left missing. When using sub-scales, if the answer to one item in a sub-scale is missing, the score is set to missing for that sub-scale.

[figure not shown]
The instrument has good evidence of content validity and psychometric properties supporting its reliability, construct validity and responsiveness (4).

- Proportion of participants with sPGA score of clear or almost clear (0 or 1) at Week 4 and 8

The following time to event endpoints will be estimated and presented using the Kaplan-Meier product-limit method:

- Time until the first achievement of PASI50, PASI75, PASI90, PASI100, sPGA of 0 or 1

Kaplan-Meier plots of time to event will also be presented. In these Kaplan-Meier plots, the line will start at 0 (since there are no event at Baseline) and will increase over time, representing time to event. The median time to event, including the two-sided 95% confidence interval, will be calculated. The estimates of the hazard ratio and 95% CI will be provided using a Cox Proportional Hazard Model stratified by the baseline PASI (≤ 20 , > 20). The censoring events include receiving selected concomitant medication or by the last assessment of targeted efficacy endpoint. The time at risk/time to event will be defined as follows:

1. If the subject has at least one event before receiving selected concomitant medication or by the last assessment of targeted efficacy endpoint, then time to event is defined as the first event date – the first dose date + 1.
2. If the subject does not have an event or receives selected concomitant medication before any event(s), the time at risk is defined as the minimum of (the last assessment date of targeted efficacy endpoint – the first dose date + 1, the date of receiving selected concomitant medication – the first dose date + 1).

3.5 MULTIPLICITY ISSUES

To control the overall Type I error of 0.05 under circumstance of multiple comparisons for the primary endpoint in the NTIP, the comparison between each dose of SAR441566 three doses (200 mg BID, 100 mg BID, 200 mg QD) and placebo will be conducted in a pairwise manner following a step-down procedure. The hierarchy will be 200 mg BID vs placebo, 100 mg BID vs placebo and 200 mg QD vs. Placebo. The testing will continue to the next level only if the previous comparison is statistically significant. The p-value (if presented) for all the other endpoints will be considered nominal since it is not under the multiplicity control.

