Overall, SAR441566 showed consistent PK and PD characteristics which support advancement into further clinical studies in participants. Both QD and BID dosing without regard to food are deemed feasible considering SAR441566  $t_{1/2z}$  of approximately 20 to 30 hours, negligible food effect at 200 mg single dose. High target occupancy was observed across the investigated dose levels in the MAD study (100 mg QD, 100/200/300 mg BID). The published estimates of TNF $\alpha$  occupancy indicate >98% for marketed TNF $\alpha$  inhibiting biologics (13) at average steady state concentration of efficacious dose. The mean TNF $\alpha$  occupancy measured on Day 14 was ~95% for 100 mg QD and at pre-dose (trough level) and ~100% for all other time points assessed across the investigated dose range, ie, at 3 hours post-dose (~Cmax) for 100 mg QD, at pre-dose and 3 hours post-dose for 100 mg, 200 mg and 300 mg BID, respectively, which is in line with the exposure-occupancy relationship established by *in vitro* studies (see also IB Section 5.1.2.4). These results suggest that 100 mg to 400 mg total daily doses can be considered potential therapeutically relevant doses. 50 mg QD is considered a sub-therapeutic dose based on the target occupancy results of doses >100 mg.

In the POM study (PDY16918) in participants with mild to moderate psoriasis, serum IL-17A, IL-17F and IL-22 levels markedly declined following 4-week treatment of 200 mg BID SAR441566, in contrast to placebo. Notably, the biomarker decreases were in line with the observed clinical improvement in TLS score of 17.7% with 90% CI [4.98 to 30.49] at Week 4 compared to placebo. The adjusted mean % improvement of 19.4% with 90% CI [6.28 to 32.48] in PASI at Week 4 was consistent with the clinically relevant improvement in the TLS score. The results obtained in the proof-of-mechanism study support the initiation of Phase 2 dose ranging studies as part of the further clinical development of SAR441566.

In summary, the dose levels selected for the current study are expected to be safe and, based on the target occupancy data from the MAD study, as well as the efficacy and biomarker outcomes from the proof-of-mechanism study, to span a range of potential therapeutically relevant as well as subtherapeutic doses which will allow to explore the dose-response relationship and the determination of the optimal therapeutic dose for future large-scale studies.

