### **9.2.5 Multiplicity adjustment**

To control the overall Type I error of 0.05 under circumstance of multiple comparisons for the primary endpoint in the NTIP, the comparison between each dose of SAR441566 three doses (200 mg BID, 100 mg BID, 200 mg QD) and placebo will be conducted in a pairwise manner following a step-down procedure. The hierarchy will be 200 mg BID vs placebo, 100 mg BID vs placebo and 200 mg QD vs. Placebo. The testing will continue to the next level only if the previous comparison is statistically significant.

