3.2.2 Main analytical approach

The individual statistical hypothesis for comparing each dose of SAR441566 vs. placebo on the primary endpoint at the two-sided significance level of 0.05 is as follows:

- Null hypothesis H0: The odds ratio between SAR441566 and placebo is equal to 1 when evaluating the primary endpoint,
- Alternative hypothesis H1: The odds ratio between SAR441566 and placebo is NOT equal to 1 when evaluating the primary endpoint.

The primary endpoint will be analyzed with the primary estimand defined according to the following attributes:

- Endpoint: Proportion of participants with a 75% or greater PASI score improvement from baseline at Week 12.
- Intervention condition: SAR441566 200 mg BID, 100 mg BID, 200 mg QD, 100 mg QD and 50 mg QD will be compared to placebo
- Analysis population: NTIP population
- Intercurrent events:
 - IMP discontinuation: it will be handled with the treatment policy strategy. The primary endpoint will be assessed based on all assessments irrespective of the IMP discontinuation.
 - Starting the selected concomitant medication (ie, prohibited/permited/rescue) (see [Table 4](#)): It will be handled with the composite variable strategy. For primary endpoint, participants who receive selected concomitant medications will be considered as non-responders for time points after the medication usage. For other participants, all available data including those collected during the off-treatment period will be used to determine the responder/non-responder status. Imputation rules of partial start dates of medication are detailed in [Section 5.6](#).

Blinded medical review of participants that receive the selected concomitant medication listed in [Table 4](#) will be performed before database lock by considering the type of medication, indication, timing, frequency, and the potential impact on efficacy to make the final decision about the list.

Table 4 - Selected prohibited/permited/rescue concomitant medications

Class of Medications	Selection Criteria	Composite variable strategy ¹
[REDACTED]		

Class of Medications	Selection Criteria	Composite variable strategy ¹

strategy. When no, a treatment policy strategy will be applied.

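### The primary-endpoint tests of 100 mg QD and 50 mg QD are neither in the step-down sequence nor labelled nominal; appending them as steps 4 and 5 would control them at no cost to the first three tests

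*SAP*

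**What the plan says.** SAP 3.2.2 frames the primary test dose by dose: "The individual statistical hypothesis for comparing each dose of SAR441566 vs. placebo on the primary endpoint at the two-sided significance level of 0.05". The intervention attribute of the primary estimand names all five active arms: "SAR441566 200 mg BID, 100 mg BID, 200 mg QD, 100 mg QD and 50 mg QD will be compared to placebo". The population-level summary in the same section covers each active arm against placebo, says that a two-sided Cochran-Mantel-Haenszel (CMH) p-value will be presented, and refers to SAP 3.5 for multiplicity.

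SAP 3.5 opens with the aim: "To control the overall Type I error of 0.05 under circumstance of multiple comparisons for the primary endpoint in the NTIP". It then gives an order of three doses: "The hierarchy will be 200 mg BID vs placebo, 100 mg BID vs placebo and 200 mg QD vs. Placebo". Protocol 9.2.5 has the same order and the same stopping rule: "The testing will continue to the next level only if the previous comparison is statistically significant". The protocol synopsis names the same three doses. SAP 3.5 closes with "The p-value (if presented) for all the other endpoints will be considered nominal since it is not under the multiplicity control".

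On the doses themselves, Protocol 4.3 says: "These results suggest that 100 mg to 400 mg total daily doses can be considered potential therapeutically relevant doses". It goes on to describe 50 mg QD as sub-therapeutic. SAP 3.2.5 adds an exploratory MCP-Mod analysis of the three QD doses and placebo on the primary endpoint, with a joint contrast test at two-sided 0.05.

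**The concern.** Two of the five primary-endpoint comparisons have no defined status. Each of 100 mg QD and 50 mg QD has a 0.05 hypothesis, a p-value to be presented and a pointer to SAP 3.5. When the reader arrives there, neither dose is in the sequence, and the nominal label is restricted to other endpoints.

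The trial is meant to identify a dose for further development (Protocol 4.1), and 100 mg QD lies within the range that Protocol 4.3 treats as potentially relevant. A p-value below 0.05 for that dose would therefore attract attention. The plan does not say whether it may be claimed within the overall 0.05. If it is read against the 0.05 in SAP 3.2.2, the error over the five comparisons exceeds 0.05. If it is not, the trial cannot make an error-controlled pairwise statement on 100 mg QD at all, although a fixed sequence would allow one without cost to the earlier steps.

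**Working it through.** **Inputs.** Overall alpha 0.05, two-sided, and the three-step order (SAP 3.5). Five comparisons, each at two-sided 0.05 (SAP 3.2.2). 24 participants per arm with 10% dropout assumed (SAP 4). PASI75 rates of 13% on placebo and 35%, 40% and 54% on 50, 100 and 200 mg QD, from the MCP-Mod sample code in SAP 5.5. The rates and power in the sample-size sections are blacked out, so the sample-code rates are an assumption here, as is 54% for the two BID arms. The binomial calculations use the unstratified chi-square test. SAP 3.2.2 stratifies the CMH test by baseline PASI.

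**1. The plan's own figure.** In a fixed sequence, any false rejection requires rejecting the first true null in the order, which happens with probability at most 0.05. For the three named doses the family-wise error is therefore 0.05. Simulation of normal statistics sharing a placebo arm (correlation 0.5, 2,000,000 runs) gives 0.0497. The stated figure is reproduced.

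**2. All five comparisons, no dose effective.** A false rejection inside the sequence requires a false rejection of 200 mg BID. The event is then p<0.05 for at least one of 200 mg BID, 100 mg QD and 50 mg QD.
- Upper bound: 3 × 0.05 = 0.15.
- If independent: 1 − 0.95³ = 0.143.
- Shared placebo, normal statistics: 0.125.
- Binomial, 24 per arm, 13% everywhere: Σ P(x₀)[1 − (1 − a(x₀))³] = 0.131. Here x₀ is the number of placebo responders and a(x₀) is the chance that one inactive arm gives p<0.05 given x₀.

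**3. First three doses effective, the two low doses inactive.**
- Upper bound: 2 × 0.05 = 0.10.
- If independent: 1 − 0.95² = 0.0975.
- Shared placebo, normal statistics: 0.091.
- Binomial: 0.095.

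**4. Superiority only.** Steps 2 and 3 count p<0.05 in either direction. Counting only false findings in favour of the drug:

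| Case | Normal | Binomial | Nominal |
|---|---|---|---|
| No dose effective | 0.063 | 0.063 | 0.025 |
| Two low doses inactive | 0.045 | 0.047 | 0.025 |

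**5. After appending 100 mg QD and 50 mg QD as steps 4 and 5.** The argument in step 1 now covers all five comparisons. The error is 0.050 in both cases by the normal calculation (0.025 for superiority). With the binomial test at 24 per arm it is 0.052 when no dose works, because the asymptotic test is slightly above its nominal size. It is 0.034 when the first three doses have 54% and the last two are inactive.

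**6. What it costs.** Probability of p<0.05 with 24 per arm and the assumed rates:

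| Comparison with placebo | As planned | Appended |
|---|---|---|
| 200 mg BID (54%) | 88.8% | 88.8% |
| 100 mg BID (54%) | 81.1% | 81.1% |
| 200 mg QD (54%) | 75.4% | 75.4% |
| 100 mg QD (40%) | 59% (uncontrolled) | 52% (controlled) |
| 50 mg QD (35%) | 45% (uncontrolled) | 33% (controlled) |

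The first three rows include the gating by earlier steps and do not change.

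**7. Dropout.** Missing responses count as non-response. If 10% dropout lowers every rate by a tenth, the first three rows become about 83%, 73% and 66%. The last two become 53% to 44% and 40% to 27%. The false-rejection figures in steps 2 and 3 become 0.128 and 0.093.

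**The case against.** The strongest defence is that the three-dose family is deliberate. The synopsis, Protocol 9.2.5 and SAP 3.5 agree on it, and the pairwise power statement in SAP 4 covers exactly those three doses. Protocol 4.3 calls 50 mg QD sub-therapeutic. The lower QD doses have their own analysis, MCP-Mod, with its own power statement. SAP 3.2.2 refers to SAP 3.5, whose reason for calling p-values nominal would apply equally to doses left out of the sequence.

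Much of this stands. Limiting confirmatory claims to three doses is a legitimate choice in phase 2. It does not settle the status of the other two comparisons, because the nominal sentence names endpoints and not doses. MCP-Mod does not fill the gap: it tests for a dose-response signal across the QD arms and does not control each pairwise comparison with placebo.

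A reader might infer that the plan breaches its stated 5% and runs at 13%. The documents do not support that. The stated 0.05 belongs to the three-dose sequence and is correct there. The 13% arises only if the two outside p-values are read as claims, which no passage says is intended, and it counts results in both directions. A reader might also infer that appending raises the prospects of the low doses. It lowers their chance of p<0.05, since they are reached only after three successes. What is gained is that a rejection is then error-controlled.

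**Conclusion.** The point holds as an omission, not as a wrong alpha. SAP 3.2.2 gives 100 mg QD and 50 mg QD a 0.05 primary-endpoint hypothesis and a p-value, and SAP 3.5 neither controls them nor calls them nominal. Read against 0.05, they would raise the error over five comparisons to about 13% two-sided (6.3% for false superiority) when no dose works. The figure is about 9.5% (4.6%) when only those two doses are inactive. These results depend little on the assumed response rates. The 52% and 33% chances of a controlled claim do depend on the sample-code rates, on 54% in the BID arms and on no dropout.

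The importance is moderate. This is a phase 2 study, its three powered comparisons are unaffected, and 50 mg QD is not expected to be effective. The reason to act is that 100 mg QD is a dose of interest and a controlled statement on it is available without loss to the other tests.

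**What to change.** In SAP 3.5, extend the order with 100 mg QD vs placebo as step 4 and 50 mg QD vs placebo as step 5, each at two-sided 0.05, stopping at the first non-significant result. Add that any primary-endpoint p-value after the stop is nominal. Record the change in SAP 3.9 as a departure from Protocol 9.2.5, before database lock. SAP 3.9 already serves this purpose for the cancelled interim analysis.

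The cost is a few sentences. No alpha, power or participants are lost for the first three comparisons. The two added doses become conditional on the earlier steps.

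If the sponsor wants only three confirmatory doses, the minimum is one clause extending the nominal sentence in SAP 3.5 to the 100 mg QD and 50 mg QD comparisons on the primary endpoint, with matching wording in SAP 3.2.2. This removes the ambiguity but gives up the controlled claim for 100 mg QD.

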3.6 SAFETY ANALYSES

All safety analyses will be performed on the safety population as defined in [Section 2](#), unless otherwise specified, using the following common rules:

- The analysis of the safety variables will be essentially descriptive, and no testing is planned.
- Safety data in participants who do not belong to the safety population (eg, exposed but not randomized) will be provided separately.

3.6.1 Extent of exposure

The extent of IMP exposure will be assessed by the duration of IMP exposure and compliance and summarized within the safety population.

Duration of IMP exposure

Duration of IMP exposure is defined as last IMP administration date – first IMP administration date + 1 days, regardless of unplanned intermittent discontinuations. If the date of the last dose of IMP is missing, the duration of IMP will be left as missing.

Duration of IMP exposure will be summarized quantitatively and categorically: 1 to 2, 3 to 4, 5 to 6, 7 to 8, 9 to 10, 11 to 12 and >12 weeks.

Additionally, the cumulative duration of treatment exposure (expressed in participant-years) will be provided.

Treatment compliance

A given administration will be considered noncompliant if the participant did not receive the number of tablets as required by the protocol.

Percentage of treatment compliance for a participant will be defined as the number of tablets that the participant has taken divided by the total number of tablets that the participant was planned to take from the first administration of IMP up to the actual last administration of IMP.

Treatment compliance will be summarized quantitatively and categorically: <80%, ≥80%.

3.6.2 Adverse events

General common rules for adverse events

All adverse events (AEs) will be coded to a lower-level term (LLT), preferred term (PT), high-level term (HLT), high-level group term (HLGT), and associated primary system organ class (SOC) using the Medical Dictionary for Regulatory Activities (MedDRA) Version 27.1.

The AEs will be analyzed in the following 3 categories:

- Pre-treatment AEs: AEs that developed, worsened or became serious during the pre-treatment period.
- Treatment-emergent adverse events (TEAE)s: AEs that developed, worsened or became serious during the treatment-emergent period
- Post-treatment AEs: AEs that developed, worsened or became serious during the post-treatment period

Similarly, the deaths will be analyzed in the pre-treatment, treatment-emergent and post-treatment periods.

The primary AE analyses will be on TEAEs. Pre-treatment and post-treatment AEs will be described separately.

An AE with incomplete or missing date/time of onset (occurrence, worsening, or becoming serious) will be classified as a TEAE unless there is definitive information to determine it is a pre-treatment or a post-treatment AE.

If the assessment of the relationship to IMP is missing for an AE, this AE will be assumed as related to IMP. Missing severity will be left as missing.

Multiple occurrences of the same event in the same participant will be counted only once in the tables within a treatment phase.

The AE tables will be sorted as indicated in [Table 5](#).

Table 5 - Sorting of AE tables

AE presentation	Sorting rules
SOC and PT	By the internationally agreed SOC order and decreasing frequency of PTs ^{a,b}
PT	By decreasing frequency of PTs ^a

a Sorting will be based on the SAR441566 200 mg BID intervention group.

b The table of all TEAEs presented by primary SOC and PT will define the presentation order for all other tables (eg, treatment-emergent SAE) presented by SOC and PT, unless otherwise specified.

Analysis of all adverse events

The overview of TEAE with the details below will be generated:

- Any TEAE
- Any treatment-emergent SAE
- TEAE leading to death
- Any TEAE leading to permanent IMP discontinuation

The AE summaries of [Table 6](#) will be generated with number (%) of participants experiencing at least one event.

Table 6 - Analyses of adverse events

Type of AE	MedDRA levels
All TEAE	Primary SOC and PT
Common TEAE ($\geq 4\%$ in at least one treatment group)	Primary SOC and PT
TEAE related to IMP as per Investigator's judgment	Primary SOC and PT
TEAE by maximal intensity	Primary SOC and PT
Treatment emergent SAE	Primary SOC and PT
Treatment emergent SAE related to IMP as per Investigator's judgment	Primary SOC and PT
TEAE leading to permanent IMP discontinuation	Primary SOC and PT
TEAE leading to death ^b	Primary SOC and PT
Pretreatment AE	Overview ^a

Type of AE	MedDRA levels
Post-treatment AE	Overview ^a
Post-treatment SAE	Primary SOC and PT

a Will include the following AE categories: any AEs, any serious AEs, any AEs leading to death, any AEs leading to permanent IMP discontinuation

b Death as an outcome of the AE as reported by the Investigator in the AE page

Analysis of deaths

In addition to the analyses of deaths included in [Table 6](#) the number (%) of participants in the following categories will be provided:

- Deaths during the treatment-emergent and post-treatment periods by main reason for death

Analysis of adverse events of special interest (AESIs)

AESIs will be selected for analyses as indicated in [Table 7](#). Number (%) of participants experiencing at least one event will be provided for each event of interest, by PT if applicable. Tables will be sorted as indicated in [Table 5](#).

Table 7 - Selections for AESIs

AESIs	Selection ^a
Pregnancy	AETERMC = 'Pregnancy' or 'Partner pregnancy' and AESI = 'Y'
Symptomatic overdose (serious or nonserious) with IMP	Symptomatic Overdose is answered Yes, with Overdose of IMP answered Yes on AE eCRF (AESI='Y' and AEOVSYMP="Y" and AEOVIMP="Y")
Symptomatic overdose (serious or nonserious) with NIMP	Symptomatic Overdose is answered Yes, with Overdose of NIMP answered Yes on AE eCRF (AESI='Y' and AEOVSYMP="Y" and AEOVOTCM="Y")
Drug abuse with IMP ^b	AESI="Y" and CMQsn00101 Drug abuse and dependence Narrow
	</

a. The list of terms may be adjusted according to MedDRA version changes

- a The list of terms may be adjusted according to MedDRA version change
- b This is not listed as an AESI in the protocol dated 25APR2024 or after

